6.4.2.1. Definition

See Section [6.3.1.1](#).

6.4.2.2. Analysis

MMRM model will be repeated for this endpoint, see Section [6.4.1.2](#).

6.4.3. Personal and Social Performance Scale (PSP) score – Change From Baseline to End of Treatment Period in Period 2**6.4.3.1. Definition**

See Section [6.3.2.1](#).

6.4.3.2. Analysis

MMRM model will be repeated for this endpoint, see Section [6.4.1.2](#).

6.4.4. Clinical Global Impression-Improvement (CGI-I) scale at End of Treatment Period in Period 2**6.4.4.1. Definition**

See Section [6.3.4.1](#).

6.4.4.2. Analysis

Analysis will be performed on the actual values (AVAL) that represent the improvement in the CGI-S at baseline as a covariate similar way presented in Section [6.3.4.2](#), on the treatment policy estimand. For this endpoint, change from baseline is not calculated because the scale scores measure change ('improvement') over time,

6.4.5. Patient Global Impression-Improvement (PGI-I) scale at End of Treatment Period in Period 2**6.4.5.1. Definition**

See Section [6.3.6.1](#).

6.4.5.2. Analysis

Analysis will be performed on the actual values (AVAL) that represent the improvement in a similar way presented in Section [6.3.4.2](#), on the treatment policy estimand. For this endpoint, change from baseline is not calculated because the scale scores measure change ('improvement') over time.

6.4.6. Schizophrenia Quality of Life Scale (SQLS) – Change From Baseline to End of Treatment Period in Period 2**6.4.6.1. Definition**

See Section [6.3.7.1](#).

6.4.6.2. Analysis

MMRM model will be repeated for this endpoint, see Section [6.4.1.2](#).

6.4.7. [REDACTED]

6.4.7.1. Definition

[REDACTED]

6.4.7.2. Analysis

[REDACTED]

7. MULTIPLE COMPARISONS AND MULTIPLICITY

any p-value associated with these comparisons will be considered as nominal and will not be used for inference.

Multiplicity adjustments will be made to p-values obtained using Rubin's rules (see Section 6.2.3).

8. SAFETY ANALYSIS

8.1. General

Safety analyses will follow the safety estimand approach using the safety analysis sets.

Safety will be assessed by qualified study personnel by evaluating reported adverse events (including serious adverse events, extrapyramidal symptoms, injection pain, injection site findings and Injection Site Reactions [ISRs]), vital signs (blood pressure, pulse and orthostatic changes, and temperature), body weight and BMI, laboratory tests, ECG, concomitant medication use, time to all-cause discontinuation, all-cause discontinuation rates and discontinuation rates due to adverse events (tolerability), time to all discontinuation by reason, and safety rating scales (including Abnormal Involuntary Movement Scale [AIMS], Barnes Akathisia Rating Scale [BARS], Simpson-Angus Scale [SAS], C-SSRS, and CDSS).

Safety assessments and time points are provided in Table 1 (for Period 1) and Table 2 (for Period 2) of the study protocol.

The safety analysis will be performed separately for Period 1 and for the integrated study periods.

The safety analysis for Period 1 will be performed by treatment group and overall (total).

The safety analysis for the integrated study periods that will be presented in the CSR and in the IDMC closed reviews, will be performed by treatment group. Specifically, for IDMC closed reviews, patients rolling over from Placebo group will be distinguished from patients who continued their active treatment assignment from Period 1. Data from Period 1 for placebo patients will not be included in the integrated summaries.

For the open sessions of the IDMC reviews, data from Period 1 and from Period 2 will be presented separately. Summary tables will be generated for each period and will only be presented as a single total column.

For the following safety variables: Adverse events, Clinical laboratory results, ECG, weight and BMI and Vital signs, a separate safety summary will be presented for the 'While on Treatment' period, defined as the period between the first IMP administration visit until and including the End of Treatment visit (including the Early Termination visit if conducted during this period). In addition a separate safety summary table and listing will be presented for the Follow-Up period, defined as the period after the End of Treatment/Early Termination visit until the end of the study.

In the case of dose adjustment (which is allowed from Visit 12 during Period 2), the patient will be regarded according to the *initial* dose they actually received in the corresponding period. In addition, separate safety summaries will be generated for AEs, SAEs, exposure to study treatment, potential clinically significant safety measures, excluding the patients with at least one dose adjustment during Period 2. Analysis may also be initiated if the results of those summaries are judged to be significantly different from the results of the safety measurements according to the *initial* actual dose. A separate set of safety tables may be generated in which the patient will be regarded according to the actual dose, by the following exposure duration: ≤ 6 months, > 6 and ≤ 12 months, > 12 months. Each patient may be calculated more than once, according to the exposure duration at each dose.

Analyses will be conducted on the raw values and changes from baseline at each time point, as appropriate. Summaries will be presented by treatment group and overall (total), unless otherwise stated.

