Following the completion of the efficacy analysis for Period 1, the Sponsor will communicate the topline results regarding TV-44749 efficacy to the Investigators. Subsequently, based on these results and guided by clinical judgment, Investigators will determine the course of action for Period 2 participants under their care. This may involve deciding whether participants will continue their current TV-44749 dose, adjusting their dose, or terminating their study participation. This also includes the option that a patient may remain on their current dose even if the population-level results indicate that the treatment arm for that dose was found futile, provided that the patient is stable on this dose and would benefit from continuing on it according to the investigator's assessment. The rationale for this approach is rooted in olanzapine's high variability, where an exposure deemed inadequate on a population level may still offer a positive risk-benefit ratio for individual patients with specific intrinsic and extrinsic characteristics affecting Olanzapine PK and patient's psychiatric stabilization and safety profile. Therefore, PI

discretion is advised when deciding on continued participation and potential dose adjustments. The possibility that one or more treatment arms may show initial failure in the topline efficacy analysis does not necessarily preclude its submission for regulatory approval. The totality of data, including secondary endpoints and sensitivity analyses, will be considered, taking into account the established efficacy of olanzapine.

It is the responsibility of the Investigator to convey the study top-line efficacy results to study participants once these become available, including the Investigator's recommendation regarding a change in TV-44749 dose or continuation of existing dose, or Investigator's decision regarding early termination. The investigator is responsible to obtain informed consent to continue participation in the study in case the participants were assigned to the dose level found to be futile. Notification of positive results to study participants, as relevant, will not require re-consent.

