10.5.6.4. Key Secondary Efficacy Analysis

10.5.6.5. Secondary Efficacy Analysis

10.5.6.6. Other Efficacy Analysis

10.6. Multiple Comparisons and Multiplicity

10.7. Safety Analysis

Safety analyses will follow the safety estimand approach using the safety analysis set.

The safety analysis will be by period with the respective randomization (for Period 1, randomization to Period 1 and for Period 2, randomization to Period 2). In addition, a safety analysis of the 2 periods together may be conducted; in this analysis, placebo patients in Period 1 will be counted as placebo, and after the randomization to Period 2, they will be assigned the actual dose in Period 2.

In case of dose adjustment, the patient may be regarded according to the randomized dose until the day of the dose adjustment, and from the first administration of the adjusted dose, the patient will be regarded according to the adjusted dose.

Safety assessments and time points are provided in [Table 1](#) and [Table 2](#).

All adverse events will be coded using the Medical Dictionary for Regulatory Activities. Each patient will be counted only once in each preferred term or system organ class category for the analyses of safety. Summaries will be presented for all adverse events (overall and by severity), adverse events related to test IMP and/or device (ie, reasonable possibility defined by the investigator as related or with missing relationship) (overall and by severity), serious adverse events, serious adverse device events, and adverse events and adverse device events causing withdrawal from the study. Summaries will be presented by treatment group and for all patients. Patient listings of serious adverse events and adverse events leading to withdrawal will be presented.

Changes in laboratory, ECG, and vital sign measurements data will be summarized descriptively. All values will be compared with predefined criteria to identify potentially clinically significant values or changes, and such values will be listed.

The use of concomitant medications will be summarized by therapeutic class using descriptive statistics.

For continuous variables, descriptive statistics (number [n], mean, standard deviation, median, minimum, and maximum) will be provided for actual values and changes from baseline to each time point. For categorical variables, patient counts and percentages will be provided.

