3.3. Safety Analysis Set

The safety analysis set for Period 1 will include all randomized patients who received at least 1 dose of TV-44749 or placebo. The safety analysis set for Period 2 will include all randomized patients to Period 2 who received at least 1 dose of TV-44749. For the integrated study periods summary tables (see Section [8](#)) the safety analysis set will include all patients in the safety analysis set of period 1 that received 1 of the 3 TV-44749 treatments groups, or all patients that meet the definition of the safety analysis set of Period 2.

In each of the safety analysis sets, treatment will be assigned based on the initial treatment patients actually received in the corresponding period, regardless of the treatment to which they were randomized, and regardless of dose adjustments, unless otherwise specified. For the integrated periods summary tables, patients randomized in Period 1 to 1 of the 3 TV-44749 groups will be counted according to the initial dose they actually received in Period 1. Patients that were randomized to Placebo in Period 1 will be counted according to the initial dose of TV-44749 they actually received after the re-randomization of those patients to the 1 of the 3 TV-44749 treatment groups in Period 2, regardless of dose adjustment that may occur during Period 2.

In cases of dosing error, a decision of what is the treatment assignment for these patients will be made in a blinded manner prior to unblinding of Period 1, as applicable. The decision will be made during the statistical data review meeting and will be documented in the statistical data review document.

For IDMC monitoring during the study, the safety analysis set will use the treatment based on the randomization assignment in the opening of each period.

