8.4. Adverse Events

Adverse events will be collected and recorded from the time a patient signs the informed consent to the end of follow-up period.

All adverse events will be coded using the Medical Dictionary for Regulatory Activities (MedDRA version 26.0 or later). Unless otherwise specified, adverse events will be summarized by SOC and preferred term, with preferred terms within SOCs presented in descending order of patient incidence. Multiple records with the same PT or SOC category and adverse event onset date for the same patient, or with overlapping or consecutive dates, are counted only once for the adverse event with the highest severity and seriousness.

Adverse events summaries will be presented for Period 1 separately and for the integrated study periods separately. Adverse events that started in Period 1 and ended in Period 2 will be reported only in Period 1, and will be presented only once in the integrated summary table.

Summaries will include treatment-emergent adverse events that are defined as adverse events that occurred at or after the first IMP injection was administered through the end of the treatment (including the assessment collected in the End-of-Treatment/ Early Termination visit).

Additional summaries will be presented for the follow-up period (after the End of Treatment/Early Termination visit and until the end of the study).

Summaries will be presented for all adverse events (overall and by severity), including adverse events defined by the investigator as related or with missing relationship to IMP treatment and/or device (overall and by severity), serious adverse events, serious adverse device events and adverse events and adverse device events causing withdrawal from the study and withdrawal from the treatment. All summaries will be presented by treatment group and overall (total), using exposure categories.

Protocol defined adverse event of special interest (PDAESI) (section 8.1.7 of the study protocol) will also be summarized and presented by treatment group and by visit..

The summary tables for adverse events will be presented by the treatment group to which the patient were assigned according to the safety analysis set. A separate summary tables will be presented, excluding the patients with at least one dose adjustment. Additional analysis may be initiated if the results of those summaries will judged by the study team to be significantly different.

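### The committed dose-adjustment check in Period 2 safety drops every dose-changer, which selects on a post-treatment event; follow-up should be censored at the first adjusted injection instead

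*SAP*

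**What the plan says.** Both documents let the investigator move a Period 2 patient to another study dose from Visit 12 (week 12) on clinical judgement (Protocol 4.1, SAP 2.1). Protocol 6.9.4 adds a second occasion, once Period 1 topline results are known: "This may involve deciding whether participants will continue their current TV-44749 dose, adjusting their dose, or terminating their study participation".

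SAP 3.3 assigns treatment in the safety sets by the initial dose actually received, "regardless of the treatment to which they were randomized, and regardless of dose adjustments, unless otherwise specified". SAP 8.1 repeats this for dose adjustment: the patient counts under the initial "dose they actually received in the corresponding period". This matches the safety estimand in SAP 1.2.5, which defines treatment as that initially received.

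Three sections commit to supplementary summaries without dose-changers. SAP 8.1 names adverse events, serious adverse events, exposure and "potential clinically significant safety measures, excluding the patients with at least one dose adjustment during Period 2". SAP 8.4 says "A separate summary tables will be presented, excluding the patients with at least one dose adjustment". SAP 8.2 does the same for exposure.

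Tables by actual dose are optional: "A separate set of safety tables may be generated in which the patient will be regarded according to the actual dose" (SAP 8.1). Protocol 10.7 is also permissive. Its sentence, introduced by *may*, ends with "from the first administration of the adjusted dose, the patient will be regarded according to the adjusted dose".

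**The concern.** Period 2 is the long-term safety phase, so its readers will want to know what happens on each dose. An initial-dose table answers a different question: what happens to patients started on a dose, whatever they receive later. It needs a companion that deals with the switch.

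The companion the SAP commits to conditions on never having switched. A patient stepped down because of an adverse event leaves that table, and the event leaves too, although it occurred at the original dose. The remaining patients are those who tolerated or responded to their dose. The dose most often reduced would then look better tolerated than it is.

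**Working it through.** **The plan's own figure.** SAP 8.2 takes a former-placebo patient with 12 injections who goes from medium to high dose at the third. It gives 2×28 − 1 = 55 days on medium and 10×28 = 280 days on high; both reproduce. The 8.2 total-exposure formula gives 11×28 + 28 = 336 days, so the example loses one day. Under the initial-dose rule all 336 days count as medium, and 280/336 = 83% of them were spent on high.

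**Earliest possible switch.** A patient on active drug throughout has injections at Visits 2, 7 and 11, then 11 more from Visit 12 to Visit 22: 11/14 = 79% fall after the switch. For a former-placebo patient it is 11/12 = 92%. These are maxima for single patients, not averages.

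**Dilution in the initial-dose table.** Let a share s of low-arm person-time be at the high dose and a share t of high-arm person-time at the low dose, with event rates L and H. The observed difference is [(1−t)H + tL] − [(1−s)L + sH] = (H−L)(1−s−t). With s = t = 10% this is 80% of the true difference; with 20% it is 60%. The formula covers low-high swaps only.

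**Loss by exclusion (all counts assumed).** Of 200 high-dose patients, 40 have the event, 20 of them are stepped down for it, and 10 others are adjusted without it. Exclusion gives (40−20)/(200−30) = 20/170 = 11.8%. Censoring at the adjusted injection keeps all 40 events: 40/200 = 20%. The initial-dose table also shows 20% here.

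**Illustrative simulation.** Assumed: 14 intervals of 28 days; event rates 0.8 (low) and 1.6 (high) per patient-year, true ratio 2.0; gamma patient heterogeneity with mean and variance 1; switching possible from the fourth injection. In the AE-driven rows only high-dose patients switch, to low. Entries are high/low rate ratios, with simulation error of about 0.01.

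| Switching assumed | High arm switching | Initial dose | Exclusion | Censoring | Dose at onset |
|---|---|---|---|---|---|
| Unrelated to AEs, both arms | 10% | 1.87 | 2.01 | 2.00 | 2.00 |
| After an AE at any earlier time | 10% | 1.93 | 1.82 | 1.96 | 1.91 |
| | 21% | 1.87 | 1.59 | 1.90 | 1.83 |
| | 35% | 1.77 | 1.20 | 1.81 | 1.70 |
| After an AE in the previous interval | 11% | 1.91 | 1.69 | 1.91 | 1.84 |
| | 24% | 1.80 | 1.28 | 1.81 | 1.68 |
| | 39% | 1.68 | 0.78 | 1.67 | 1.50 |

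When events drive switching, exclusion is the worst of the four and can reverse the ordering. Censoring is closer to the truth in every such row, but it is not unbiased and does about as well as the initial-dose table. Attribution by dose at onset is no better than initial dose in those rows.

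**The case against.** The exclusion tables are supplementary. The main table keeps every patient, and the event that prompts a first step-down is filed there under the dose at which it occurred. Initial-dose grouping stays close to the randomized comparison and is the declared estimand. All of this stands, and it is why the main analysis should not change.

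Four stronger readings are tempting, and the documents do not support them.

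- A reader might infer that the SAP dropped a protocol rule to split follow-up at the adjusted dose. Protocol 10.7 says only that this may be done, and SAP 8.1 keeps the option.
- A reader might infer that exclusion is the only firm information on dose changes. SAP 8.4 commits to dose at onset in its listings of serious events, events leading to discontinuation or withdrawal, and deaths. SAP 8.2 commits to injection counts by dose, and to actual cumulative exposure if the proportion of dose-changers is high (not defined). None of these gives event rates by dose, but they are commitments.
- A reader might infer that the actual-dose tables are never produced if the first two sets agree. The condition about results being judged different governs a separate sentence in SAP 8.1. The actual-dose sentence is optional but states no precondition.
- A reader might infer that committee monitoring has the same flaw. SAP 3.3 says that for the monitoring committee "the safety analysis set will use the treatment based on the randomization assignment in the opening of each period", but report details sit in a charter that is not available here.

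The objection that actual-dose tables are imperfect also stands. Administrative Letter 03 (Protocol Appendix N) gives a terminal half-life of about 11 days and complete elimination at 50 to 55 days. At 28 days per interval, that is 1.8 to 2.0 dosing intervals of mixed exposure after a switch.

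**Conclusion.** The point holds for the integrated-period tables. The committed supplementary summaries select on a post-treatment event and discard adverse events that occurred at the original dose. The bias arises only if switching relates to tolerability or response. That is plausible, since changes follow clinical judgement and possibly topline results, but it is not established. Its size cannot be estimated, because neither document gives a switching rate; every percentage of switching above is an assumption. With switching unrelated to events the exclusion tables are sound, and the initial-dose tables are merely diluted as a measure of safety on a dose. Period 1 safety is untouched, because no dose can change before week 12.

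**What to change.** In SAP 8.1, 8.2 and 8.4, replace the exclusion of dose-changers with summaries of all patients, follow-up censored at the first adjusted injection, with exposure-adjusted rates. Keep the initial-dose tables as the main analysis.

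In addition, turn the optional actual-dose output into a commitment: adverse event, serious adverse event and potentially clinically significant value tables by dose at onset, with person-time by dose, the number and direction of dose changes by arm, and a stated rule for attributing events soon after a switch. Label these tables descriptive.

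The cost is SAP wording and one extra table set. Dose adjustments are already in the CRF, and dose at onset is already needed for the listings. Patients will contribute to more than one dose column, which SAP 8.1 and 8.2 already accept. Informative censoring and depot carry-over remain and should be stated with the results.

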8.2. Duration of Exposure to Study Drug

Duration of exposure to study drug (days) for individual patients will be calculated during the integrated study periods as the number the days patient was exposed to treatment (last day of TV-44749 administration – first day of TV-44749 administration + 28). For patients randomized to placebo in Period 1 who were re-randomized to Period 2, the first TV-44749 injection is at Visit 11 (week 8), the day of re-randomization for Period 2.

Duration of treatment (days) will be summarized for integrated study periods using descriptive statistics. Summaries of the total exposure to TV-44749, will be presented by treatment group, and for overall (total) for patients on active treatment. For an individual patient who was assigned to the placebo group in Period 1, the total duration of exposure will be counted only in Period 2 (the exposure to placebo in the first 8 weeks will not be included in the summary).

Duration of exposure (days) will also be presented by number of injections for the integrated periods using the mutually exclusive categories:

- 0 injections
- 1 injection
- 2 injections
- ≥ 3 to ≤ 6 injections
- ≥ 7 to ≤ 9 injections
- ≥ 10 to ≤ 12 injections
- > 12 injections

In addition, summary of exposure to study TV-44749 doses will be calculated using the categories:

- < 6 months
- ≥ 6 to < 12 months,
- ≥ 12 months.

The total number of TV-44749 injections by dose and overall (total) will be presented. Exposure categories including at least 6 and 12 months are defined as at least 6 and 12 injections plus 28 days following the last injection, respectively.

All summary tables for duration of exposure will be presented by treatment group and overall (total).

Unless otherwise specified, in cases where there was a dose adjustment, exposure will be calculated according to the *initial* actual dose received in Period 1 (or the initial actual dose received in Period 2) regardless of dose adjustments. In addition, separate safety summaries will be generated, excluding the patients with at least one dose adjustment event during the study.

If the results of those summaries are judged to be significantly different from the results of duration of exposure summaries according to the randomized dose, additional analyses will be conducted. These analyses may include shift tables of randomized dose to dose adjustments. If the proportion of patients with dose adjustment will be high, additional table according to the actual cumulative exposure by dose will be presented. For this table a patient may contribute to more than 1 dose level, and the duration of exposure at each dose will be determined by the time from 1st administration of the dose to the day of the dose adjustment minus 1 or the last administration, as appropriate. For example if a patient that was re-randomized to medium dose following placebo in Period 1, and then underwent a dose adjustment to the high dose for the 3rd injection, this dose will be used until the end of study. Thus, assuming that all injections are administered exactly 28 days apart, the patient will contribute $2*28-1= 55$ days to the medium dose group, and $28*10=280$ days to the high dose group.

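### SAP 8.2's by-dose exposure rule omits the 28 days after the last injection, giving 252 days where its own example states 280; the optional tables in 8.1 also use opposite boundaries at 6 and 12 months

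*SAP*

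**What the plan says.** SAP 8.2 defines total exposure as "last day of TV-44749 administration – first day of TV-44749 administration + 28", so 28 days are credited after the last injection. It defines its month categories in the same spirit: "Exposure categories including at least 6 and 12 months are defined as at least 6 and 12 injections plus 28 days following the last injection". The middle category is "≥ 6 to < 12 months", with below 6 and 12 or more on either side.

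The section then adds a conditional output: "If the proportion of patients with dose adjustment will be high, additional table according to the actual cumulative exposure by dose will be presented". In that table a patient may contribute to several doses, and time on each dose is "the time from 1st administration of the dose to the day of the dose adjustment minus 1 or the last administration, as appropriate". A worked example follows at once. A patient on placebo in Period 1 is re-randomized to the medium dose, moves to the high dose at the 3rd injection and stays on it, with injections exactly 28 days apart. The example credits 2 × 28 − 1 = 55 days to the medium dose and 28 × 10 = 280 days to the high dose.

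SAP 8.1 says that a separate set of safety tables by actual dose may be produced, split by exposure duration as "≤ 6 months, > 6 and ≤ 12 months, > 12 months". It does not define a month.

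**The concern.** The by-dose rule offers two end points. For a dose that was changed, it is the day before the change. For the last dose received, it is the last administration. Nothing adds the 28-day interval after that final injection, although both the main formula and the example include it. A programmer working from dates cannot satisfy both the sentence and the example. Copying the example's 28-per-injection count is not a full answer either, because SAP 2.1 allows dosing visits to move by ±3 days, and exceptionally up to 5 days early, so a correct date rule is needed.

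The table is meant to show how long patients were on each dose actually given. A fixed loss of 28 days falls entirely on the last dose and is proportionally largest where that dose was given only a few times.

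The two sets of month bands treat ties in opposite ways. A tie at 12 is not an oddity here: 12 injections is the planned Period 2 maximum (Protocol 1.1), and so the most TV-44749 that a former-placebo patient can receive.

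**Working it through.** **Inputs.** Up to 12 Period 2 injections (Protocol 1.1); 28-day spacing, two medium-dose injections and then the high dose (SAP 8.2 example); main formula and by-dose rule (SAP 8.2). With day 0 at visit 11, injections fall on days 0, 28, …, 308. The medium dose is given on days 0 and 28, the high dose on days 56 to 308 (10 injections).

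**The example, from the rule as written.**
- Medium: 56 − 0 − 1 = 55. This reproduces.
- High: 308 − 56 = 252, or 253 counting both end days. The stated 280 does not reproduce.
- High with the main formula's tail: 308 − 56 + 28 = 280. This reproduces exactly.

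The literal rule would give 280 only with 11 high-dose injections (10 × 28), which means 13 in Period 2, more than the planned 12. Taking the 3rd injection as the third of the whole study does not help, because the example's 55 days require two medium-dose injections first.

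**Totals for this patient.**

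| Method | Medium | High | Total |
|---|---|---|---|
| Rule as written | 55 | 252 | 307 |
| Worked example | 55 | 280 | 335 |
| Main formula, 308 − 0 + 28 | – | – | 336 |

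The one day between 335 and 336 comes from the minus 1 at the change.

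**Size by number of injections.** If the last dose has j injections, the rule gives 28(j − 1) days and the main convention 28j, a shortfall of 1/j. Changes are allowed from visit 12 and visit 22 is the last dosing visit, so with one change and full dosing j runs from 1 to 11:
- j = 1: 0 against 28 days (100% short)
- j = 3: 56 against 84 (33%)
- j = 10: 252 against 280 (10%)
- j = 11: 280 against 308 (9%)

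A patient who never changes dose is affected too: 12 injections give 308 days by the rule and 336 by the main formula.

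**Month bands.** On schedule, 6 injections cover 5 × 28 + 28 = 168 days and 12 cover 11 × 28 + 28 = 336 days.

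| Injections of one dose | 8.2 | 8.1 |
|---|---|---|
| 6 (168 days) | ≥6 to <12 | ≤6 |
| 12 (336 days) | ≥12 | >6 to ≤12 |

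The 8.1 placement is the same whether a month is 28 days (168 = 6 × 28; 336 = 12 × 28) or a calendar month (168 < 182.6; 336 < 365.25).

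**The case against.** The best defence is that the intent is visible. The example comes directly after the rule, the 28-day convention stands in the same section, and both lead to 280. On that view this is an omitted term that a careful programmer would supply. That is fair, and it limits the consequence: the 28-day loss arises only if the sentence is followed instead of the example. It does not make the sentence right, and the phrase leaving the end point to what is appropriate only selects one of two dates; it adds no days.

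Four stronger readings should be resisted.
- A reader might infer that the minus 1 is an arithmetic error. Rule and example agree on it (55 days), so it is a stated convention whose cost is one day of non-additivity per change. Protocol 10.7, under which "from the first administration of the adjusted dose, the patient will be regarded according to the adjusted dose", assigns patients to a dose for safety analysis and is worded as something that may be done. It is not a day-count rule.
- A reader might infer that the month labels are wrong because 12 injections span 48 weeks. The 8.2 categories are expressly defined by injections, so relabelling is a preference.
- A reader might infer that every fully dosed former-placebo patient is classified differently in 8.1 and 8.2. That needs dosing exactly on schedule and no dose change. If a month in 8.1 is 28 days, a net delay of one day (337 days) puts a 12-injection patient above 12 months, in agreement with 8.2.
- A reader might infer that total exposure is miscounted. The main formula carries the 28 days and is sound.

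It is also true that the two sets of bands belong to different outputs and that nothing in the SAP requires them to match. That makes the boundary point an inconsistency in reporting and not an error of calculation.

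**Conclusion.** The by-dose rule is wrong as written: 252 days against the SAP's own 280, short by 28 days on each patient's last dose, and zero days for a dose given only at the final injection. This rests on reading the rule literally; the on-schedule figures assume 28-day spacing, as the example does. The boundary mismatch between 8.1 and 8.2 is real for exactly 6 or 12 on-schedule injections of one dose, and depends on what 8.1 means by a month once dosing drifts.

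The consequence is modest. The by-dose table appears only if dose adjustment is common, the 8.1 tables are optional, and all are descriptive. Efficacy and type I error are not touched. It should be corrected before the tables are programmed.

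**What to change.** **By-dose rule.** Define exposure to a dose as the sum over its continuous dosing episodes. An episode that ends in a dose change runs from its first administration to the first administration of the next dose. The final episode is last minus first administration within that episode, plus 28. The example becomes (56 − 0) + (308 − 56 + 28) = 56 + 280 = 336, equal to the main formula.

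Working by episode matters because a patient may return to an earlier dose. Take medium on days 0 and 28, high on days 56 to 112, and medium again on days 140 to 308. Last minus first plus 28 over the whole medium dose gives 336; with 140 − 56 = 84 for high, the total is 420 against a true 336. By episode, medium is 56 + (308 − 140 + 28) = 252 and high is 84, total 336.

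If the minus 1 is kept, state that by-dose days fall one day short of total exposure for each dose change, and leave the example's 55.

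**Bands.** In the 8.1 actual-dose tables, use the 8.2 boundaries (<6, ≥6 to <12, ≥12 months) and the 8.2 definition by injections.

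**Cost.** SAP wording only; no new data. Against the rule as written, by-dose exposure rises by 28 days per patient on the last dose and by 1 day per dose change. In 8.1, patients with exactly 6 or 12 on-schedule injections of one dose move up one category.
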